### **8.3.2. Method of Detecting AEs and SAEs/AESIs**

The method of recording, evaluating, and assessing causality of AEs and SAEs/AESIs and the procedures for completing and transmitting SAE/AESI reports are provided in [Section 10.3](#).

Care will be taken not to introduce bias when detecting AEs and/or SAEs/AESIs. Open ended and nonleading verbal questioning of the participant is the preferred method to inquire about AE occurrences.

### **8.3.3. Follow-up of AEs and SAEs/AESIs**

After the initial AE/SAE/AESI report, the investigator is required to proactively follow each participant at subsequent visits/contacts. All SAEs/AESIs will be followed until resolution, stabilization, the event is otherwise explained, or the participant is lost to follow-up (as defined in [Section 7.3](#). Further information on follow-up procedures is given in [Section 10.3](#).

### **8.3.4. Regulatory Reporting Requirements for SAEs/AESIs**

Prompt notification by the investigator to the sponsor regarding an SAE/AESI is essential so that legal obligations and ethical responsibilities towards the safety of participants and the safety of an IMP under clinical investigation are met.

The sponsor has a legal responsibility to notify both the local health authority and other health authorities about the safety of an IMP under clinical investigation. The sponsor will comply with country-specific regulatory requirements relating to safety reporting to the health authority, IRBs/IECs, and investigators.

Investigator safety reports must be prepared for suspected unexpected serious adverse reactions according to local regulatory requirements and sponsor policy and forwarded to investigators as necessary.

An investigator who receives an investigator safety report describing an SAE/AESI or other specific safety information (eg, summary or listing of SAEs/AESIs) from the sponsor will review, acknowledge, and then file it along with the IB and will notify the IRB/IEC, if appropriate, according to local requirements.

### **8.3.5. Pregnancy**

Details of all pregnancies in female participants or in female partners of male participants will be collected after the start of IMP and until final contact.

If a pregnancy is reported, the investigator should inform the sponsor within 24 hours of learning of the pregnancy and should follow the procedures outlined in [Section 10.4.2](#).

Abnormal pregnancy outcomes (eg, spontaneous abortion, fetal death, stillbirth, congenital anomalies, ectopic pregnancy) are considered SAEs.

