**Table 1: Schedule of Assessments**

Trial Periods/Phases	Screening (up to 4 weeks) a		Treatment									Follow-up (4 weeks)		
			Titration (2 weeks)			Maintenance (12 weeks)								
Visit/Contact	Screening/ Visit 1	Baseline/ Visit 2		Telephone Contact	Visit 3	Telephone Contact	Visit 4	Telephone Contact	Visit 5	Telephone Contact	Visit 6	Visit 7 (Telephone)	Visit 8 (Telephone)	Visit 9
Day	-28 to -2	-1	1	7	14	28	42	56	70	84	98/ET b	101	105	131
Window				±3 days								±1 day	±3 days	
Entrance and History														
Informed consent	X													
Review inclusion/exclusion criteria	X	X c,d												
Medical and psychiatric history e	←-----→													
MINI	X													
Demography	X													
History of drug and alcohol use	X													
Nicotine use and history	X	X			X		X		X		X			
Review of birth control methods	X	X			X		X		X		X			X
Breathalyzer test for alcohol f	X	X												
eDiary training	X													
Efficacy Assessments														
Review eDiary including compliance with use of eDiary		X		X	X	X	X	X	X	X	X	X	X g	
PDSS	X	X					X		X		X			
CGI-S		X			X		X		X		X			
Other Assessments														
SDS		X					X				X			

Trial Periods/Phases	Screening (up to 4 weeks) a		Treatment									Follow-up (4 weeks)		
			Titration (2 weeks)			Maintenance (12 weeks)								
Visit/Contact	Screening/ Visit 1	Baseline/ Visit 2		Telephone Contact	Visit 3	Telephone Contact	Visit 4	Telephone Contact	Visit 5	Telephone Contact	Visit 6	Visit 7 (Telephone)	Visit 8 (Telephone)	Visit 9
Day	-28 to -2	-1	1	7	14	28	42	56	70	84	98/ET b	101	105	131
Window				±3 days								±1 day	±3 days	
HAM-A		X			X		X		X		X			
EQ-5D-5L		X									X			
Safety Assessments														
Height (Screening only) and weight	X	X					X				X			
Physical/neurological examination h	X	X									X			
ECG i	X	X					X				X			
Vital signs j	X	X			X		X		X		X			
C-SSRS	X	X			X		X		X		X			
PWC											X k	X	X	
Prior/concomitant treatments l	←-----→													
Adverse event monitoring m			←-----→											
Laboratory														
Blood for safety laboratory	X	X			X		X		X		X			X
Serum pregnancy test n	X													
Urine pregnancy test n		X			X		X		X		X			X
Urine for safety laboratory	X	X									X			
Urine drug screening o	X	X			X		X		X		X			

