Trial Periods/Phases	Screening (up to 4 weeks) a			Treatment								Follow-up (4 weeks)		
				Titration (2 weeks)		Maintenance (12 weeks)								
Visit/Contact	Screening/ Visit 1	Baseline/ Visit 2		Telephone Contact	Visit 3	Telephone Contact	Visit 4	Telephone Contact	Visit 5	Telephone Contact	Visit 6	Visit 7 (Telephone)	Visit 8 (Telephone)	Visit 9
Day	-28 to -2	-1	1	7	14	28	42	56	70	84	98/ET b	101	105	131
Window				±3 days								±1 day	±3 days	
Screening only laboratory tests: hepatitis B, C, HIV, and serum FSH p,q	X													
PK blood sample f					X		X		X		X			
Blood sample for future biospecimen research s		X												
Other														
IMP dispensing		X t			X		X		X					
Dosing starts			X											

Abbreviations: BID=twice daily; CGI-S=Clinical Global Impression-Severity of Symptoms Scale; C-SSRS=Columbia-Suicide Severity Rating Scale; ECG=electrocardiogram; EQ-5D-5L=European Quality of Life; ET=early termination; FSH=follicle-stimulating hormone; HAM-A=Hamilton Anxiety Scale; HIV=human immunodeficiency virus; IMP=investigational medicinal product; MINI=Mini International Neuropsychiatric Interview; PCR=polymerase chain reaction; PDSS=Panic Disorder Severity Scale; PK=pharmacokinetic; PWC=Physician's Withdrawal Checklist; SDS=Sheehan Disability Scale.

a Participants will enter a Screening Period of at least 14 days and up to 28 days.

b If a participant discontinues early, the participant should follow the safety follow-up procedures (Visits 7-9).

c Review of inclusion/exclusion criteria includes review of eDiary data to assess panic attack frequency.

d Inclusion/exclusion criteria will be assessed at Baseline to ensure ongoing participant eligibility, with the exception of age or assessments that are only scheduled during Screening (eg, height for body mass index calculation).

e Medical occurrences that begin before the start of dosing with IMP but after obtaining informed consent should be collected as medical and/or psychiatric history.

f A breathalyzer alcohol test is required at the Screening Visit and at Baseline. The alcohol test (breathalyzer or blood/urine) can be conducted at any time during the trial at the discretion of the investigator.

g The eDiary will be collected through Visit 8 (Day 105). Physical devices will be collected at the last in-person visit.

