### 5.1. Inclusion Criteria

Individuals are eligible for participation in this trial only if all of the following criteria apply:

1.	Male and female participants, ages 18-65 years, inclusive, at the time of Screening.
2.	Primary diagnosis of panic disorder based on the DSM-5-TR criteria (present for at least 6 months prior to the Screening Visit) and confirmed by the MINI; additional primary diagnosis of agoraphobia is allowed and secondary diagnosis of GAD and/or SAD is allowed.
3.	Participant has had a minimum of 8 panic attacks, with no week free of panic attacks, in the month prior to the Screening Visit. In the 14 days preceding the Baseline Visit, the participant must have had at least 4 panic attacks and no week free of panic attacks. Note: Participant must complete a minimum of 11 eDiary day entries in the 14 days preceding the Baseline Visit.
4.	Participants with a PDSS total score $\geq 12$ at the Screening and Baseline Visits
5.	Body mass index of 17.5 to 40.0 kg/m  and a total body weight >48 kg at Screening.
6.	A female participant of childbearing potential who is sexually active with a nonsterilized male partner must agree to use a highly effective method of contraception (defined in Section 10.4.1.2 ) from signing of informed consent throughout the duration of the trial until the last dose of IMP and for an additional 33 days after the last dose. A male participant with a pregnant or a nonpregnant partner of childbearing potential must agree to use a condom during treatment and until the last dose of IMP and for an additional 93 days. In addition, male participants should not donate sperm for a minimum of 93 days following last dose of IMP.
7.	Capable of giving signed informed consent, which includes compliance with the requirements and restrictions listed in the ICF and in the trial protocol.
8.	Ability, in the opinion of the investigator, to understand the nature of the trial and comply with protocol requirements, including the prescribed dosage regimens, scheduled visits, laboratory tests, and other trial procedures.

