#### **10.4.2. Collection of Pregnancy Information**

##### **10.4.2.1. Male Participants With Partners Who Become Pregnant**

- The investigator will attempt to collect pregnancy information on any male participant's female partner who becomes pregnant while the male participant is in this trial. This applies only to male participants who receive trial intervention.
- After obtaining the necessary signed informed consent from the pregnant female partner directly, the investigator will record pregnancy information on the appropriate form and submit it to the sponsor within 24 hours of learning of the partner's pregnancy. The female partner will also be followed to determine the outcome of the pregnancy. Information on the status of the mother and child will be forwarded to the sponsor. Generally, the follow-up will be no longer than 6 to 8 weeks following the estimated delivery date. Any termination of the pregnancy will be reported regardless of fetal status (presence or absence of anomalies) or indication for the procedure.

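### Partner-pregnancy collection ends at final contact, about 33 days after the last dose, while the restrictions on men run to 93 days; outcome follow-up of later reports is unclear (minor, cheap to fix)

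*Protocol*

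**What the plan says.** **Restrictions on men.** Under Protocol 5.1, criterion 6, a man with a pregnant partner or a partner of childbearing potential "must agree to use a condom during treatment and until the last dose of IMP and for an additional 93 days". The criterion adds that "male participants should not donate sperm for a minimum of 93 days following last dose of IMP". The first is a condition of entry; the second is worded as advice.

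**Collection of pregnancies.** Protocol 8.3.5 says that details of pregnancies in women in the trial or "in female partners of male participants will be collected after the start of IMP and until final contact". The next sentence carries no end date: "If a pregnancy is reported, the investigator should inform the sponsor within 24 hours of learning of the pregnancy". It then sends the site to 10.4.2.

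**The procedure for partners.** Section 10.4.2.1 applies to a "female partner who becomes pregnant while the male participant is in this trial", and only where the man received trial treatment. With the partner's consent, the pregnancy is followed to its outcome: "Generally, the follow-up will be no longer than 6 to 8 weeks following the estimated delivery date".

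**End of participation.** Sections 4.1.3 and 4.1.4 put the last visit (Visit 9, Day 131) about 33 days after the last dose. Table 1, footnote b, sends participants who stop early through the same Visits 7 to 9. The Table 1 row "Review of birth control methods" has an entry at Visit 9. No contact is scheduled after it.

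**The concern.** For women the two periods agree: contraception runs for 33 days after the last dose, and so does contact. For men they do not. Section 2.3 names fetal toxicity and impaired spermatogenesis and male fertility among the potential risks, and contraception among the measures against them. A partner conception within 93 days of the last dose is an event that the male restriction is meant to prevent, yet collection ends with 60 of those days still to run.

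Two things are at stake. Late conceptions may not come to the site's attention. And if one does, sites may differ on whether 10.4.2.1 lets them approach the partner for consent and follow the pregnancy to outcome. Normal outcomes would then tend to be missing, which makes any abnormal one harder to interpret.

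**Working it through.** **Inputs from the documents**
- Last planned dose: Day 98 (Table 1, footnote t).
- Final visit: Visit 9, Day 131 (4.1.4).
- Male restriction: 93 days after the last dose (5.1, criterion 6).
- Female contraception: 33 days after the last dose (same criterion).
- Planned size: about 123 per group (1.1).

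**Step 1: reproduce the protocol's own interval.** 131 − 98 = 33 days, which matches the roughly 33 days in 4.1.3.

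**Step 2: the gap.**
- Women: 33 − 33 = 0 days.
- Men: 93 − 33 = 60 days, that is, days 34 to 93 after the last dose. For a man who completes dosing, the restriction ends on Day 98 + 93 = Day 191, and 191 − 131 = 60. As a share of the post-dose restriction, 60/93 = 64.5%. This is a share of days, not of events.
- Table 1 as extracted shows no clear window for Visit 9. If it may move by 3 days either way (an assumption), the gap is 57 to 63 days.
- Men who stop early have the same 60-day gap, provided that Visit 9 falls about 33 days after their last dose.

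**Step 3: what happens to a conception in those 60 days.**
- 8.3.5, first sentence: outside the collection period.
- 8.3.5, second sentence: if the site is told, it should notify the sponsor within 24 hours and turn to 10.4.2.
- 10.4.2.1: read literally, it does not apply, because the man has left the trial. The basis for partner consent and outcome follow-up is therefore unclear.
- 8.3.1 and 10.3.3: an SAE learned of after the trial and judged related is reported, and 10.3.3 has it followed. Section 8.3.5 counts abnormal pregnancy outcomes as SAEs, so these have a route. An uneventful pregnancy does not. Section 8.3.1 says investigators need not seek events after participation ends.
- 10.4.2.2: the explicit text on post-trial pregnancy-related SAEs sits under female participants and has no counterpart in 10.4.2.1.

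**Step 4: how many events.** The documents give no sex ratio, partner status, conception rate or actual number randomized, so these inputs are assumptions: 30–50% men; 30–60% of them with a partner who could conceive; 2–15% pregnancies per couple-year with condom use.

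Expected events on darigabat = n × share men × share with such a partner × yearly rate × 60/365.25, where 60/365.25 = 0.1643.
- Low, n = 123: 123 × 0.30 × 0.30 × 0.02 × 0.1643 = 0.036.
- High, n = 123: 123 × 0.50 × 0.60 × 0.15 × 0.1643 = 0.909.

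| n on darigabat | Low | High |
|---|---|---|
| 123 (planned; upper bound) | 0.04 | 0.91 |
| 61.5 (half) | 0.02 | 0.45 |
| 30.75 (a quarter) | 0.01 | 0.23 |

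**The case against.** The strongest case against raising this has four parts.

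1. *Late reports and serious outcomes already have a route.* The second sentence of 8.3.5 is open-ended, and 8.3.1 and 10.3.3 cover related SAEs after the trial. This stands. A reader might infer that pregnancies conceived after Visit 9 would go unreported; the documents do not support that. What remains is narrower: no scheduled enquiry, and no clear procedure for following a late pregnancy that involves no related SAE.

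2. *The rest of the paperwork is unseen.* A reader might also infer that nobody asks men about late partner pregnancies. The consent pages were removed, and the Operations Manual and pregnancy form are not part of these documents; any of them may ask. The claim has to be limited to what the visible protocol schedules.

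3. *The windows need not be equal.* The protocol gives no reason for the 93 days, and 2.3 does not say that exposure through the father harms a pregnancy. This also stands: aligning the windows is a sensible choice, not a requirement found in the documents. The case rests on the protocol's own restriction, not on a demonstrated hazard.

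4. *The gain is small.* Every scenario in the table is below one event, and SAP 1 and SAP 6 report early closure with the planned size not reached. A reminder at Visit 9 helps only men who have not yet passed it and does not make the last 60 days actively monitored. This is correct and fixes the weight of the point, but the wording problem in 10.4.2.1 remains and costs almost nothing to correct.

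**Conclusion.** The mismatch is real and minor. Routine collection of partner pregnancies stops about 33 days after the last dose, against a 93-day restriction on men. The last 60 days have no scheduled enquiry in the visible protocol, and outcome follow-up of a late report is unclear. The passive routes soften this without closing it.

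The 60 days follow directly from the protocol's dates. The event estimate rests on assumed inputs and is below one on darigabat even at full planned enrolment, which was not reached. Sample size, power and efficacy conclusions are unaffected. This is a cheap improvement to safety reporting, not a flaw in the trial's evidence. Confidence is medium, because the consent form and manuals may already ask men to report.

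**What to change.** - **8.3.5 and 10.4.2.1:** extend reporting and outcome follow-up to any partner pregnancy conceived between the start of IMP and 93 days after the last dose, in men who received IMP, including those the site learns of after Visit 9. Keep the existing form, partner consent and outcome follow-up. This also covers a conception shortly before Visit 9 that is recognised only afterwards.
- **Visit 9:** at the birth-control review already scheduled, ask men to tell the site of any such pregnancy.
- **Consent form:** add the same request if it is not already there.

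This needs no extra visit, test or staff. The downside is an occasional late report that needs partner consent and follow-up to 6 to 8 weeks after the estimated delivery date. For a conception on Day 191 that is up to 38 + 8 = 46 weeks later, taking 38 weeks from conception to delivery as an assumption.

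Coverage after Visit 9 would be prompted self-report. Active coverage of all 60 days would need a further contact near Day 191, which the expected number of events hardly justifies. If all men are already past Visit 9, a short memo to sites on handling late reports would serve the same purpose.

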### **8.3.6. Treatment of Overdose**

An overdose is defined as a known deliberate or accidental administration of investigational drug, to or by a trial participant, at a dose above that which is assigned to that individual participant according to the protocol. Please refer to the darigabat Investigator's Brochure for more detailed information about overdose.

There is no specific antidote for overdose with darigabat. In the event of overdose, treatment should consist of general supportive measures.

In the event of an overdose, the investigator should:

- Contact the medical monitor immediately.

- Closely monitor the participant for any AE/SAE and clinically significant vital sign, ECG, or laboratory abnormalities. Additional safety procedures may need to be performed at the investigator's discretion.
- Document the quantity of the excess dose as well as the duration of the overdose (if multiple time points) in the eCRF.

Decisions regarding dose interruptions or modifications will be made by the investigator in consultation with the medical monitor based on the clinical evaluation of the participant.

### 8.3.7. Adverse Events of Special Interest

All AESIs should be reported according to the procedures and timelines for SAEs (see [Section 10.3.4](#)).

The following events will be reported as AESIs:

- AEs that result in the discontinuation of IMP
- AEs potentially related to abuse (refer to the Abuse Potential Monitoring Plan [APMP] document for details)
- AEs of suicidality
- C-SSRS (Since Last Visit) "Yes" answer to Suicidal Ideation Items #4 or #5 or any Suicidal Behaviors
- QTcF >500 ms or an increase >60 ms from Baseline
- Liver enzymes:
  - ALT or AST  $\geq 3 \times$  ULN and serum bilirubin  $\geq 2 \times$  ULN (suspected Hy's Law)
  - ALT  $\geq 5 \times$  ULN
- Hematologic abnormalities:
  - Absolute neutrophil count  $< 1.5 \times 10^9/L$
  - Platelet count  $< 100 \times 10^9/L$
  - Hemoglobin  $< 10$  g/dL

For QTcF, liver enzymes, and/or hematological abnormalities meeting the above AESI criteria, a repeat evaluation should be immediately performed for confirmation and the medical monitor notified. See [Section 10.6.1](#) for further details on the assessment of elevations in liver test results.

If the repeat evaluation is confirmed abnormal, the treatment with study drug should be discontinued and the early termination visit should be completed.

An APMP will be used to monitor events that may suggest that darigabat produces drug effects that could be sought out for abuse purposes. As part of the APMP, AEs potentially related to abuse and medication handling irregularities related to suspected or known abuse of IMP must be reported as AESIs. Investigators and site staff at each trial site will be trained on reporting potentially abuse-related AEs. While the investigators will be provided with examples of AE

terms as a guide during trial conduct, the analysis of potentially abuse-related AEs will be based on a search by the sponsor of all relevant MedDRA terms, all verbatim terms, and any open text fields within the AE data to identify text strings suggestive of abuse potential, consistent with US FDA guidance ([US FDA Guidance for Industry, 2017](#)).

#### **8.4. Pharmacokinetics**

With participants maintaining their normal BID dosing routine, a single daytime venous blood sample for determination of plasma darigabat concentration will be collected as specified in the Schedule of Assessments ([Section 1.3](#)).

During each PK sampling, an approximately 4-mL venous blood sample will be collected into appropriately labeled tubes. The blood samples will be used to provide approximately  $2 \times 1$ -mL plasma samples (one primary and the other as backup) for separate quantifications in plasma.

Plasma samples will be processed, stored, and shipped to the bioanalytical facility according to the instructions provided to the investigator in advance of the trial. Additional details about sample collection, processing, and shipment will be provided in the PK manual.

A fully validated bioanalytical method will be used to quantitate the concentrations of darigabat in plasma. Plasma samples collected in this trial may be used for further development of the bioanalytical method or identification of metabolites. The backup samples may be stored for a duration of approximately up to 1 year after the date of the final CSR.

Plasma concentration data from this trial combined with other data may also be used to build and/or update a population PK model for darigabat for the purpose of further characterizing the PK or PK/PD behavior of the compound. Any population PK assessment will be described in a separate report.

Statistical analyses of PK parameters are summarized in [Section 9.3.6](#).

#### **8.5. Biomarkers**

Biomarkers are not evaluated in this trial.

#### **8.6. Future Biospecimen Research**

Studying the variation in genetic markers and other biomarkers may help to explain some of the variability in response seen with some drugs among different individuals. This is referred to as pharmacogenomic/biomarker research. Comparing the DNA, RNA, protein, and metabolite variation patterns of participants who respond well and those who respond poorly to treatment may help to better define the most appropriate group of participants in which to target a given treatment. Collecting biospecimens for exploratory pharmacogenomic/biomarker analyses and retaining them at Cerevel makes it possible to better understand the drug's mechanism of action and to seek explanations for differences in, for example, exposure, pharmacodynamics, tolerability, or safety not anticipated prior to the beginning of this trial.

Future biospecimen research samples will be collected from participants who provide additional consent specifically for this sample collection. Research performed on these samples may include genetic analyses, gene expression profiling, proteomics, metabolomics and/or the

measurement of other analytes. Such research is for biomarker testing to address emergent questions not described elsewhere in the protocol (as part of the main trial). The objective of collecting these specimens is to explore and identify biomarkers that inform the scientific understanding of diseases or their therapeutic treatments.

Additional details about future biospecimen research samples are provided in [Section 10.5](#).

